Appendix M: Patient Script Inviting Remote Tool Viewing w/ Test Results

Hello, my name is [YOUR NAME] and I am a clinical research assistant at City of Hope is there a [([name]) PATIENT NAME] here?

Hi Mr/Ms. [PATIENT NAME]. I am reaching out to you because you recently agreed to participate in our HOPE-Genomics study, in which patients are receiving and reviewing their genetic test results through our HOPE-Genomics App or website. Does this sound familiar?

[IF NO] That's okay, I can provide you with a quick summary.

For this study you were approached by me or another clinical research assistant either in clinic or via phone to be consented in a study, that your physician or genetic counselor may have mentioned to you in your appointment. For this study we are testing our HOPE-Genomics app or website with patients to help patients review their genetic test results. After this initial consent, you may have completed a survey about cancer and genetics at the clinic or chosen to complete it at home on paper or through a survey link. Does this sound familiar?

[IF STILL NO] thank them and end the call.

[IF YES] Great. First, thank you very much for participating in our study. I am contacting you because the next phase of your participation in the study is to review your genetic tests results via our tool. Did you receive your login information via email?

[IF NO] That's okay, I can provide you with that information now.

[PROVIDE LOGIN INFORMATION]

[IF YES]

Have you had an opportunity to view the tool?

[IF NO]

Are you having any trouble accessing the tool?

[IF YES]

We would be happy to assist you troubleshoot this issue now. Do you have a few minutes to do so now?

[IF NO]

I would be happy to schedule an appointment to discuss this in the next few days. Unfortunately, we have had some recent procedural changes at our institution due to COVID-19, which limit our ability to meet with patients in person. As such, we are primarily meeting with patients via web conference (i.e. Zoom) or phone. Would you like to schedule a time to meet with one of our study staff?

Protocol 02/17/2023

HOPE-Genomics Clinical Trial

Protocol Packet: 13

[IF YES]

Great! Thank you so much for accommodating us. [SCHEDULE TIME]

[IF NO] Thank them for the participation thus far and let them know that unfortunately we cannot continue with the study unless they have access to the tool. Rest assured that all the information you provided for this study will be removed.

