4.3 Tool Access and Patient Pre-Education Survey

After enrollment, all participants will be provided with a hard-copy or electronic educational pamphlet about whole-exome sequencing (WES). Patients in the Return of Results plus Pre-test Education arm will be provided with login and dual-factor authentication instructions and have immediate access to educational content in the tool, with their sequencing results to become available in the tool shortly after their results are available in Epic. Patients in the Return of Results Only arm will not be able to see tool content until their genomic test results are available (e.g., ~2-6 weeks after sample collection). Patients in the Usual Care arm will have access to the tool content after completing all study surveys, approximately ~9 months after their sequencing results are available.

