4.4 Results Disclosure

We expect results to be available within ~3-14 days of sample acquisition. We will monitor the patients' laboratory data to see when results have been finalized. Lab results and variant interpretations for the HOPE Genomics intervention will be stored in a custom genomic database designed by COH Research Informatics. All results will be validated by study staff before data are input into the HOPE-Genomics tool. All clinicians will receive results through the EHR. Additionally, clinicians with patients in the intervention arm will also be able to view their patients' results through the HOPE-Genomics after individual-level patient data have been entered into HOPE-Genomics. Results will be available to patients in the HOPE-Genomics app approximately 3-14 days after they are available in the EHR.

At this time, we will ask patients in the Return of Results Only intervention arm, (Arm 2) and the Return of Results + Pre-Test Education arm (Arm 3) to log into the HOPE-Genomics tool on their own time. Study staff will provide patients with instructions to create an account and log into the tool using dual-factor authentication. Study staff will track patients' tool access through Google Analytics and call or send automated RedCap reminders to encourage tool use, if necessary. Study staff will track patients' tool access through Google Analytics and call and/or send automated REDCap reminders to encourage tool use, if necessary. In addition, the study staff will be available to help patients access HOPE-Genomics at subsequent clinic/infusion visits or via secure web conference at any point in time following the disclosure of their test results until the end of the study (with coordination with the study team).

Patients in the control arm (Arm 1) will have their results returned in clinic by their provider, with no changes to the clinician's typical delivery method. Patients will be provided an educational pamphlet that generally describes sequencing and will granted access to the HOPE-Genomics tool with their results after completing all follow-up study surveys, approximately 9 months after their results are in the EHR.

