4.5 Follow up Surveys

4.5.1 10-Day Follow-Up Survey

All patients enrolled in the study will be asked to complete a follow-up survey approximately 10 days after results are released in the EHR. The survey will either be mailed to the participant, provided electronically and/or by text message via REDCap survey link or completed over a scheduled phone or Zoom call with a staff member, according to patient preference. If the survey is mailed, the patient will be provided with a return envelope. Follow-up survey reminders will be similar to those outlined for the baseline survey. The follow-up survey outcomes are detailed in Table 1. For participants of both intervention arms, the survey will also include questions about the usability of HOPE-Genomics. Survey measures will be similar to measures detailed in Section 4.1.1.

Patients in Arm 1 (usual care) will receive a modified survey that does not contain questions that pertain specifically to the HOPE-Genomics tool, like usability.

4.5.2 3 Month Follow-Up Survey

Delivery of the follow-up survey and study materials will follow similar procedures mentioned in Section 4.3.1. The 3 Month follow-up survey outcomes are detailed in Table 1. Survey measures will be similar to measures detailed in Section 4.1.1.

4.5.3 9 Month Follow-Up Survey

Delivery of the follow-up survey and study materials will follow similar procedures mentioned in Section 4.4.1. The 9 Month follow-up survey outcomes are detailed in Table 1. Survey measures will be similar to measures detailed in Section 4.1.1. Participants in the Usual Care Arm will view their results in the HOPE-Genomics tool after completing the 39Month Follow-Up Survey. None of their follow-up surveys will contain questions pertaining to the HOPE-Genomics tool or its usability.

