8.7 Participant Withdrawal from Research

At any time after signing the informed consent document, participants may elect to withdraw from participation in this protocol as follows: A participant may (1) withdraw from future study activities but permit clinical data collection to continue, (2) withdraw from future study activities and disallow the collection of clinical data, (3) remain amenable to study activities but disallow retention of PHI data, or (4) elect to withdraw completely from the study whereby all data will no longer be made available for research. Participant withdrawal, including the nature of withdrawal, will be documented in the Master List which will be kept in a password-protected file, accessible only by authorized study staff using secure COH computers. The request to withdraw from studies will also be documented in the patient's medical record via Epic. If they do not wish to participate but are interested in exploring other options such as talking with their care team or a social worker, we will provide appropriate referrals.

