Appendix Q: HOPE-Genomics Withdrawal Email Template

Dear Mr./Ms./Dr. [PATIENT'S NAME],

Thank you for letting us know about your decision to withdraw from the HOPE-Genomics study! We completely understand, and truly appreciate your interest in our study.

To document withdrawal and protect your personal information, City of Hope requires you to complete the attached withdrawal form at your earliest convenience. I have attached the form to this email, and I will also mail you a physical copy of the form with a return envelope.

You can either mail or scan the completed form back to us or schedule a time to complete the form with us over the telephone. Please let us know what is most convenient for you so we can facilitate the withdrawal process as soon as possible.

If you have any questions about completing the withdrawal form, please email [contact], or call the Principal Investigator, [name] at [contact] or the Clinical Research Coordinator, [name] at [contact]. You can also reach the Institutional Review Board at City of Hope by calling [contact].

Thank you very much again for your participation!

The HOPE-Genomics Team

[name], [name], [name], [name], and [name]

Division of Clinical Cancer Genomics

Medical Oncology and Therapeutics Research

Department of Population Sciences

City of Hope Comprehensive Cancer Center

[name]

[name]

Appendix R: Patient Survey Link Text Message Script (Baseline/Pre-study/10 day/3 month/9 month for Intervention Arms)

Dear [Insert Patient Name]

This is the HOPE-Genomics Team from City of Hope.

This is a reminder to complete the **[Title of Survey]** at your earliest convenience.

You can access the survey by clicking this link **[insert link]** and entering the provided study ID: **[Insert patient study ID number]**.

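### A branch of the Appendix M call script ends participation and removes survey data for some tool-arm patients only, against sections 4.5.1 and 8.7 (minor)

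*Combined protocol and SAP*

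**What the plan says.** Appendix M is the call script for patients who have been invited to see their results in the tool. It asks whether they have viewed it and then "Are you having any trouble accessing the tool". It offers help on the call or, failing that, an appointment. The last [IF NO] branch tells staff to explain that "unfortunately we cannot continue with the study unless they have access to the tool" and to add: "Rest assured that all the information you provided for this study will be removed".

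Other parts of the protocol bear on this:

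- **Section 4.5.1:** "All patients enrolled in the study will be asked to complete a follow-up survey approximately 10 days after results are released in the EHR". The timing runs from the record release, not from viewing. Sections 6.0 and 6.2.1 place the primary recall outcome at this survey.
- **Section 8.7:** a participant may choose among four levels of withdrawal. Only in the fourth does the participant "elect to withdraw completely from the study whereby all data will no longer be made available for research".
- **Section 4.4:** staff can help with access "at any point in time following the disclosure of their test results until the end of the study".
- **Appendix Q:** written for a patient who has decided to leave; it says "City of Hope requires you to complete the attached withdrawal form".
- **Section 4.3:** "Patients in the Usual Care arm will have access to the tool content after completing all study surveys". Sections 4.1 and 4.4 agree.
- **Appendices H and K:** H places the follow-up survey after viewing. K, the follow-up invitation for the intervention arms, thanks the patient for having viewed the results in the tool.

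**The concern.** The branch ends participation after randomisation because the patient has not got into the assigned intervention. Arm 1 has no tool to access until its surveys are complete, so no usual-care patient can be removed this way while survey outcomes are still being collected. Patients who cannot get into a web tool and turn down help may also be those who recall their results less well. Taking them out of Arms 2/3 and leaving their counterparts in Arm 1 would then shift the recall comparison toward the tool.

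The loss would be permanent. Section 4.4 puts results in the tool about 3 to 14 days after they reach the record, so the call may come before or after the 10-day survey. The script would either stop that survey being collected or delete answers already given, and no later sensitivity analysis could use them.

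**Working it through.** **1. Who the branch reaches.** The nesting of the [IF YES] and [IF NO] steps is not marked. Read in sequence, the branch applies to a patient who has not viewed the tool, reports trouble with access, has no time to fix it on the call and declines an appointment. Read loosely, it applies to any non-viewer who declines an appointment. The sequential reading fits better, because the stated condition is access rather than viewing.

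**2. Against the rest of the protocol.**

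- Section 4.5.1: direct conflict. A patient removed by the script is enrolled but would not be surveyed.
- Section 8.7: direct conflict on data. Complete removal is the participant's election; the script offers no choice.
- Section 4.4: a tension. Help is offered to the end of the study, but the text does not say what follows if it is declined.
- Appendix Q: a tension. It requires a form but covers only a patient's own decision to leave.

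**3. The planned power.** Inputs from section 6.2.1: 39% recall in Arm 1 (n = 130), a gain of 15 points to 54% in Arms 2/3 (n = 260), two-sided alpha 0.05. Pooled two-proportion z-test:

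- pooled rate = (130 × 0.39 + 260 × 0.54)/390 = 0.49
- null SE = √[0.49 × 0.51 × (1/130 + 1/260)] = 0.0537
- alternative SE = √[0.39 × 0.61/130 + 0.54 × 0.46/260] = 0.0528
- power = Φ[(0.15 − 1.96 × 0.0537)/0.0528] = Φ(0.848) = 80.2%

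The stated 80% is reproduced.

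**4. Bias if the branch is used.** Let f be the share of Arms 2/3 removed and g the recall of retained minus removed patients. The documents give neither, so both are assumptions. With no true effect, overall recall of 0.39 = (1 − f) × R + f × (R − g), so retained recall R = 0.39 + f × g and the spurious difference is f × g.

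Example, f = 0.10 and g = 0.20: R = 0.41, retained n = 260 × 0.90 = 234, null SE 0.0537, alternative SE 0.0535. Rejection probability = Φ[(0.02 − 0.1052)/0.0535] + Φ[(−0.02 − 0.1052)/0.0535] = 0.0558 + 0.0097 = 6.5%.

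| Share removed | Spurious difference, g = 10 / 20 points | Type I error, g = 10 / 20 points |
|---|---|---|
| 2% | 0.2 / 0.4 points | 5.0% / 5.1% |
| 5% | 0.5 / 1.0 points | 5.1% / 5.4% |
| 10% | 1.0 / 2.0 points | 5.4% / 6.5% |
| 20% | 2.0 / 4.0 points | 6.5% / 11.1% |

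With g = 0 the error stays at 5.0% for every share.

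**5. What the shares mean in patients.** Removal would act on enrolled patients. Section 6.1 enrols 155 per arm, so Arms 2/3 hold 2 × 155 = 310; the 260 is what remains after attrition. Shares of 2, 5, 10 and 20% are therefore about 6, 16, 31 and 62 patients. If removals are instead counted within the planned loss, so that 260 are still analysed, the 10% row becomes 5.4% / 6.6% and the 20% row 6.6% / 11.6%. The picture does not change.

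**The case against.** The strongest reply is that this is one line in an appendix, in a branch that few patients would reach, and that the protocol body overrides it. Much of that stands. At 2-5% removed the type I error is at most 5.4%. A 20% share would exceed the 10% attrition that section 6.1 assumes from all causes. The material directly after the branch and the consent pages were not available for this check, and terms on staff ending participation could sit there. Section 8.7 says what participants may choose; it does not say that nobody else may end participation. The removal of data is therefore the firmer half of the conflict with that section.

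A reader might also infer more than the documents support:

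- **That the primary analysis drops non-users.** Section 6.2.1 speaks of exposure to the tool, but it names Arms 2/3 and gives n = 260, which is two of three equal arms. That reads as assignment.
- **That the Aim 2 analysis is compromised.** Information a patient provided does not plainly include data abstracted from the record, and section 6.2.2 specifies intention-to-treat. An effect on later abstraction is conjecture.
- **That patients have been lost this way.** Nothing in the documents shows that the branch was ever used.

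The reply does not remove the conflict with sections 4.5.1 and 8.7. It holds on either reading of the branch; only the number of patients reached changes.

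**Conclusion.** The concern holds as a minor inconsistency with a one-sided consequence. As written, Appendix M contradicts section 4.5.1 on who is surveyed and section 8.7 on who decides that data are removed, and it sits poorly with section 4.4 and Appendix Q. Before the survey outcomes are collected it can act only in Arms 2/3.

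The size of any bias cannot be known from the documents. It depends on an assumed removal share and an assumed recall gap, and it vanishes if removed patients recall as well as the rest. On the sequential reading the low shares are the relevant ones, and there the inflation is negligible. Extreme inputs give alarming figures: with 20% removed, all recalling at only 10%, type I error would be 25.6%. Nothing in the documents supports such inputs, so the trial should not be described as having a seriously inflated error rate.

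**What to change.** 1. Delete from Appendix M the lines saying that the study cannot continue and that the information will be removed.
2. Keep non-viewers in all surveys and in record abstraction unless they elect withdrawal under section 8.7.
3. Reword Appendix H so that the follow-up survey does not depend on viewing, and Appendix K so that it does not presume viewing.
4. State in section 6.2.1, and in the matching 3-month text of section 6.2.3, that Arms 2/3 are analysed as randomised. This only clarifies what the text already implies.
5. Report by arm how many patients, if any, have already been removed under the script. Give counts only, since those patients were told that their information would be removed.

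These are wording changes plus one count. Deleting the lines will not recover answers already removed.

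The statistical cost is dilution. If only users gain 15 points, tool-arm recall is 0.39 + 0.15 × (1 − share not using). At 130 against 260, power falls from 80% to 76% with 5% non-use (recall 53.25%) and to 71% with 10% (recall 52.5%). Section 4.5.1 already requires these patients to be surveyed, so the stated design carries this cost in any case.

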Appendix N: Patient Incentive Letter

[DATE]

Dear Mr./Ms. [LAST NAME],

This is the HOPE-Genomics Team from City of Hope. We are writing to you because you recently received your genomic testing results and completed a follow-up survey as part of our research study at the City of Hope Comprehensive Cancer Center. Thank you so much for participating – your feedback has been very helpful thus far!

Enclosed, please find your [INSERT \$ AMOUNT] gift card as a thank you for your participation so far.

If you have any questions about this research study, please call [CONSENTER'S NAME] at [INSERT CONSENTER'S PHONE NUMBER], or the Principal Investigator, [name] at [contact] or the Clinical Research Coordinator, [name] at [contact]. You can also reach the Institutional Review Board at City of Hope by calling [contact].

Thank you very much again for your participation!

The HOPE-Genomics Team

[name], [name], [name], [name], and [name]

Division of Clinical Cancer Genomics

Medical Oncology and Therapeutics Research

Department of Population Sciences

City of Hope Comprehensive Cancer Center

[name]

[name]

Appendix O: Patient Knowledge Answers & Genomic Information Letter

[DATE]

Dear [Patient Name],

This is the HOPE-Genomics Team at City of Hope. We are writing to you because you recently participated in our research study at The City of Hope. In the research study we are developing ways to teach patients about cancer and genomic testing. For this study, you completed a short survey about cancer and genetics. Thank you so much for participating – your responses have been very helpful!

On your survey, you indicated that you would like to receive information on cancer genomic testing, as well as the correct answers to the survey questions about genetics. In the enclosed package, we are including both an information sheet that has resources and links for cancer genomic testing, as well as a copy of the correct answers for the genetics questions from the survey.

If you have any questions about this research study, please call [CONSENTER'S NAME] at [INSERT CONSENTER'S PHONE NUMBER], or the Principal Investigator, [name] at [contact] or the Clinical Research Coordinator, [name] at [contact]. You can also reach the Institutional Review Board at City of Hope by calling [contact].

Thank you very much again for your participation!

The HOPE-Genomics Team

[name], [name], [name], [name], and [name]

Division of Clinical Cancer Genomics

Medical Oncology and Therapeutics Research

Department of Population Sciences

City of Hope Comprehensive Cancer Center
[name]
[name]

Information on Cancer Genomic Testing

What is cancer genomic testing?

Genomic testing is the process of looking closely at your genes. Genes are the instructions to make everything in our bodies work. Some genes can tell us how tall we will be or our eye color. Other genes help us fight cancers. Genes are made up of an instructional code, called “DNA”.

Your doctor might order cancer genomic testing from two places (and sometimes, both!):

1. **Cancer cells (i.e. DNA from a tumor).** These usually come from a biopsy sample. Looking at genes from your cancer cells can help your medical team find more options, and/or understand the prognosis (forecast or likely course of your cancer).
2. **Normal cells (i.e. DNA from non-cancer cells).** These usually come from a blood sample or cheek cells. Testing these can clarify if your family members may be at higher risk for cancer, and help you and your care team figure out how to potentially reduce cancer risk for yourself and your family members.

When testing either cancer or normal cells, it is possible it may not find helpful information, and at times may not work. It is up to you and your care team to decide if testing is right for you, and what types of testing might be helpful.

The following are general questions about cancer and genetics	
1. Cancer is uncontrolled cell growth.	True
2. All cancers are aggressive.	False
3. Cancer is caused by a combination of inheritance, environmental, and lifestyle factors.	True
4. Hereditary (inherited within families) forms of cancer are common.	False
5. Any genetic change within a cell will give rise to cancer.	False
6. Cancers are usually caused by a change to a single gene.	False
7. All cancers have the same gene changes.	False

The following questions ask about how genetic testing can be used in cancer care.

In general, genetic testing can be used to...

8. Confirm a cancer diagnosis (tell where in the body a cancer started)	True
9. Find out the cancer “stage” (for example, stage I or stage IV)	False
10. Help select a cancer treatment	True
11. Determine exactly when a person will develop cancer.	False
12. Help predict if a cancer treatment will work.	True

13. Help select a research study (clinical trial)	True
14. Help to confirm if a cancer treatment is working.	True
15. Find out where cancer is located in the body (for example, in the lung or colon)	False
16. Help predict if a person has a better or worse than average outlook (prognosis) than other patients who have the same type of cancer	True
17. Find out if the cancer has spread beyond where it started in the body	False
18. Find out if a person's family members might have an increased risk of developing cancer	True
19. Help predict the chances that the cancer will come back after treatment	True
20. Find out if a person has an increased risk of developing cancer	True
21. Find out if a person (and possibly their family members) have a higher risk of developing a health condition other than cancer (for example heart disease or high cholesterol).	True

The following questions ask about your understanding of the differences between genetic testing in CANCER CELLS and NORMAL CELLS.

22. Finds gene changes that a patient was born with	Normal Cells
23. Finds gene changes that have happened over a patient's lifetime	Cancer Cells
24. Can be used to help select a cancer treatment for a patient	Both
25. Can reveal information about a patient's risk of developing cancer in the future	Both
26. Finds gene changes that are NOT inherited and that cannot be passed from parents to children	Cancer Cells
27. Can reveal results that have unknown health implications	Both
28. Commonly can suggest health risks for a patient's family members	Normal Cells

Genes	29. Genes are made of DNA	True
	30. Genes affect health by influencing the proteins our bodies make	True
	31. All of a person's genetic information is called his or her genome.	True
	32. A person's genes change completely every 7 years.*	False
	33. The DNA in a gene is made of four building blocks (A, C, T, and G).	True

	34. Everyone has about 20,000 to 25,000 genes.	True
Genes and health	35. Gene variants can have positive effects, harmful effects, or no effects on health.	True
	36. Most gene variants will affect a person's health.*	False
	37. Everyone who has a harmful gene variant will eventually have symptoms.*	False
	38. Some gene variants have a large effect on health while others have a small effect.	True
	39. Some gene variants decrease the chance of developing a disorder.	True
	40. Two unrelated people with the same genetic variant will always have the same symptoms.*	False
How genes are inherited in families	41. Genetic disorders are always inherited from a parent.*	False
	42. If only one person in the family has a disorder it can't be genetic.*	False
	43. Everyone has a chance for having a child with a genetic disorder.	True
	44. A girl inherits most of her genes from her mother while a boy inherits most of his genes from his father.*	False
	45. A mother and daughter who look alike are more genetically similar than a mother and daughter who do not look alike.*	False
	46. If a parent has a harmful gene variant, all of his or her children will inherit it.*	False
	47. If one of your parents has a gene variant, your brother or sister may also have it.	True
Whole Exome Sequencing	48. Whole exome sequencing can find variants in many genes at once.	True
	49. Whole exome sequencing will find variants that cannot be interpreted at the present time.	True
	50. Whole exome sequencing could find that you have a high risk for a disorder even if you do not have symptoms.	True
	51. Your whole exome sequencing may not find the cause of your disorder even if it is genetic.	True
	52. The gene variants that whole exome sequencing can find today could have different meanings in the future as scientists learn more about how genes work.	True
	53. Whole exome sequencing will not find any variants in people who are healthy.	False

Resources

Cancer Genomics

What is Cancer Genomics? (NIH):

<https://cancergenome.nih.gov/cancergenomics/whatisgenomics/whatis>

- Has video explaining genetic basis of cancer

- Has links to Cancer Genomics Overview and Research

American Cancer Society Genetics and Cancer: <https://www.cancer.org/cancer/cancer-causes/genetics.html>

Medical Genetics 101: http://www.ashg.org/education/medical_genetics.shtml

General Support

Genetic Counseling

- National Society of Genetic Counselors: <http://www.nsgc.org/page/aboutgeneticcounselors>
- Find a Cancer Genetics Clinician (NIH): <https://www.cancer.gov/about-cancer/causes-prevention/genetics/directory>
- KinTalk: <http://kintalk.org/>
- My Family Health Portrait: <https://familyhistory.hhs.gov/FHH/html/index.html>

Cancer Therapy Evaluation Program (NIH): <https://ctep.cancer.gov/default.htm>

My Cancer Genome: <https://www.mycancergenome.org/>

CancerCare: <https://www.cancercare.org/>

ASCO Resources (fact sheets, planning, caregiving): <https://www.asco.org/practice-guidelines/resources-patients>

ACS Resources (diagnoses, treatment options): <https://www.cancer.org/treatment.html>

